4 STUDY DESIGN

4.1 OVERALL DESIGN

Single-center, single-masked (the individual(s) performing efficacy and safety measures will be masked to treatment assignment for the patient(s) they are assessing), vehicle-controlled, randomized, parallel group study. For all dose groups a screening visit will be followed by a baseline visit 14 days later (qualification period). At the end of the qualification period patients who still exhibit signs of MGD and who can comply with dosing instructions at the baseline visit will be enrolled into a 3-month treatment period.. At the baseline (Day 0) visit, patients will be randomly assigned in a 2:2:1:1 ratio to receive either AZR-MD-001 1.0% ointment/semi-solid drug or AZR-MD-001 1.0% ointment/semi-solid drug plus Hylo-Forte® or AZR-MD-001 vehicle or AZR-MD-001 vehicle plus Hylo-Forte® for twice-weekly evening administration for 3 months. Where applicable, Hylo-Forte® will be dosed approximately 5 minutes before study ointment. The study flow is shown in Figure 1.

Clinical study AZ201801, Amendment 3 is an ongoing multicenter, double-masked, vehicle-controlled, randomized, parallel group study carried out in 2 sequentially overlapping cohorts (Cohort 1: sequential rising concentrations of AZR-MD-001 ointment/semi-solid drug (i.e., Cohort 1, Group 1-0.1%, Cohort 1, Group 2-0.5%, Cohort 1, Group 3-1.0%, and Group 4-0.1%, 0.5%, 1.0%, or 2.5%) and AZR-MD-001 vehicle dosed twice-weekly and/or once daily in the evening; Expansion Cohort: parallel doses of up to two concentrations of AZR-MD-001 ointment/semi-solid drug (i.e., two of four available concentrations: 0.1%, 0.5%, 1.0%, or 2.5%) and AZR-MD-001 vehicle dosed either twice-weekly or once daily in the evening. For Cohort 1 patients will be randomized in a 4:1 ratio (AZR-MD-001: Vehicle) and in the Expansion Cohort patients will be randomized in a 1:1:1 ratio (see Section 2.2 for more detail on the study).

Clinical study SOVS2019-070 is an ongoing single-center, double-masked, vehicle-controlled, randomized study to evaluate the efficacy, safety and tolerability of AZR-MD-001 1.0% in participants with contact lens discomfort (CLD). During this study, some tolerability issues were observed, with three participants experiencing adverse events which led to discontinuation from the study. All findings were consistent with prior reported adverse events for AZR-MD-001 and selenium sulfide and were reversable upon discontinuation of treatment.

Based upon these findings, patient's antidotal reports of improved tolerability with nighttime application, and the successful use of artificial tears before dosing to improve tolerability, it is desirable to investigate different methods to improve the safety and tolerability of AZR-MD-001 1.0% in patients with MGD, who are the target population for this treatment.

4.3 END OF STUDY DEFINITION

A participant is considered to have completed the study if he or she has completed all scheduled visits including the last visit or the last scheduled procedure shown in the Schedule of Activities (SoA), Section 1.3.

5 STUDY POPULATION

The study will consist of patients with Meibomian Gland Dysfunction (MGD).

5.1 INCLUSION CRITERIA

- Male or female, 18 years of age or older at screening visit
- Capable of understanding and willing to provide written informed consent and likely to complete the entire course of study according to instructions
- Written authorization for use and release of health and research study information has been obtained
- Best-corrected visual acuity (BCVA) of 20/40 or better (Snellen equivalent), using the logarithm of the minimum angle of resolution (LogMAR) in each eye at the screening visit
- Evidence of meibomian gland obstruction (based on a meibomian gland secretion (MGS) score of ≤ 12 for 15 glands of the lower lid) in both eyes at the baseline visit
- Reported dry eye signs and symptoms within the past 3 months: Ocular Surface Disease Index (OSDI) score ≥ 13 ; TBUT < 10 seconds in both eyes
- Demonstrated ability to follow dosing instructions at the baseline visit
- Prior to the screening visit patients are required to discontinue:
 - Use of systemic antihistamines or isotretinoin for at least 1 month
 - Anti-inflammatory treatments for DED (e.g., cyclosporine ophthalmic emulsion [Restasis® or Ikervis®] or lifitegrast ophthalmic solution [Xiidra®]) for at least 3 months
 - All other prescription medications used for dry eye or MGD (e.g., antibiotics, corticosteroids, and non-steroidal anti-inflammatory drugs) for at least 2 weeks
 - LipiFlow® or other lid-heating therapy, meibomian gland probing, or therapeutic gland expression in either eye within 6 months prior to the screening visit
 - All other MGD treatments (e.g., at-home warm compress therapy, eyelid hygiene, eyelid massage, and manual lid expression) for at least 2 weeks

And

- Women of childbearing potential must have a history of bilateral tubal ligation or use oral contraceptives, implants, injectables, transdermal patch, or intrauterine

device for birth control during the study. Abstinence is considered a reliable method of birth control. If these methods of birth control do not apply, women of childbearing potential must have a monogamous partner who has had a vasectomy at least 3 months before the screening visit or who is of the same gender.

5.2 EXCLUSION CRITERIA

- Uncontrolled ocular disease (except for MGD) or uncontrolled systemic disease
- Patient has glaucoma or ocular hypertension as demonstrated by an intraocular pressure (IOP) in either eye at screening of ≥ 24 mm Hg determined by Goldman applanation tonometry or has planned insertion/removal of glaucoma filtration shunts/devices during the study
- Corneal abnormality or disorder that impacts normal spreading of the tear film (keratoconus, pterygia, scarring) or corneal integrity
- BCVA worse than 20/40 in either eye at the screening visit
- Current use of punctal plugs, anticipated insertion during the study, or a history of punctal cautery in either eye at any time prior to the baseline visit or anticipate such a procedure during the study
- Keratoconjunctivitis sicca secondary to destruction of conjunctival goblet cells as occurs with vitamin A deficiency or scarring, such as that with cicatricial pemphigoid, alkali burns, Stevens-Johnson syndrome, trachoma, or irradiation
- Keratoconjunctivitis sicca secondary to aqueous deficient DED
- Active ocular infection (bacterial, viral, or fungal) at the screening visit
- Corneal, conjunctival, or eyelid inflammation (including allergic, vernal, or giant papillary conjunctivitis and mucous membrane pemphigoid) that in the judgment of the investigator may interfere with the study results or the ability of subjects to complete the treatment period
- Recent (within the past 3 months of the baseline visit) ocular surgery, trauma, herpes, or recurrent inflammation
- Contact lens use anticipated during the study
- Periocular application of makeup during the study or tattooing of the lids
- Use of any type of scleral lenses or sealed compartment ocular frames within 2 months of the screening visit, or planned use during the study
- Use prohibited medications (topical, topical ophthalmic, systemic and/or injectable) during the appropriate pre-study wash-out period and during the study

- Unwilling to abstain from the use of systemic medications known to cause dryness for the study duration that is not used on a stable dosing regimen for at least 30 days prior to the screening visit
- Unwilling to abstain from the use of systemic or topical treatments for MGD or dry eye for the study duration (Including over-the-counter [OTC] artificial tears, ocular lubricants, or dietary supplements known to impact ocular surface health [e.g., Omega 3 supplements] except those prescribed for use as part of the study)
- Eyelid abnormalities that affect normal lid function in either eye other than those caused by meibomian gland dysfunction
- Diagnosis of hepatitis C infection, human immunodeficiency virus (HIV) infection, sarcoidosis, amyloidosis, active tuberculosis, or graft versus host disease
- Known carrier of infectious disease
- History of anterior segment surgery or trauma that could affect corneal sensitivity (e.g., cataract surgery or any surgery involving a limbal or corneal incision) in either eye within the 12 months prior to the screening visit
- Planned anterior segment surgery (e.g., cataract surgery or any surgery involving a limbal or corneal incision) in either eye during the study period
- Known allergy or sensitivity to fluorescein, lissamine green, or the study medication or its components
- Use of medicated shampoos containing selenium (e.g., Selsun Blue, Exsel, Selsum, and Seleen) following the screening visit
- Patient is unlikely to follow study instructions or to complete all required study visits or has a condition or situation that in the investigator's opinion, may put the patient at significant risk, may confound the study results, or may interfere significantly with the patient's participation in the study
- Patient is an employee at the investigational site or is related to any member of the study staff
- Pregnant, nursing, or females of childbearing potential and not utilizing adequate birth control measures, or planning pregnancy
- Participation in another clinical trial involving a therapeutic drug or device within the past 30 days (except for AZR-MD-001)
- Epilepsy or history of migraines exacerbated by flashing, strobe-like lights
- Meibography score at the screening visit of 4 (greater than 75% partial glands using the gestalt grading system)
- Corneal staining ≥ 3 (between 33 and 100 dots) using the Oxford Scheme
- Schirmer's tear test without anesthesia ≤ 5 seconds in either eye at the screening visit

5.3 LIFESTYLE CONSIDERATIONS

To be eligible for this study patient must comply with the following:

- Patients should not have LipiFlow® or other lid-heating therapy, meibomian gland probing, or therapeutic gland expression in either eye within 6 months of the baseline visit or during the study.
- Patients must have discontinued (2 weeks before baseline) and be willing to remain off other MGD treatments (e.g., at-home warm compress therapy, eyelid hygiene, eyelid massage, and manual lid expression) during the study (except those prescribed for use as part of the study).
- Patients should not have punctal plugs or plan to have punctal plugs inserted during the study.
- Patients must have discontinued (1 month before baseline) and be willing to remain off antihistamines or isotretinoin during the study.
- Patients must have discontinued (3 months before baseline) and be willing to remain off Anti-inflammatory treatments for DED (e.g., cyclosporine ophthalmic emulsion [Restasis® or Ikervis®] or lifitegrast ophthalmic solution [Xiidra®]).
- Patients should avoid the use of medicated shampoos containing selenium (e.g., Selsun Blue, Exsel, Selsum, and Seleen) following the baseline visit.
- Patients must have discontinued (2 weeks before baseline) and be willing to remain off all other prescription medications used for dry eye or MGD (e.g., antibiotics, corticosteroids, and non-steroidal anti-inflammatory drugs) during the study.
- Patients must avoid periocular application of makeup during the study

Patients should be instructed to strictly follow the visit schedule and to report any changes in condition to the investigative site personnel.

The patients should be instructed to maintain a stable dose of any concomitant medication used chronically, or any new medication initiated during the study if possible. Patients should be instructed to communicate any changes to their medication at their next study visit. Patients should also be reminded to contact the study site if they experience difficulties during their study participation.

Patients should refrain from using any ophthalmic preparations other than study treatment in order to obtain an accurate assessment of their signs and symptoms. Patients should be instructed to communicate any changes to their ophthalmic preparations other than study treatment at their next study visit.

5.4 SCREEN FAILURES

Screen failures are defined as participants who consent to participate in the clinical trial but are not subsequently randomly assigned to the study intervention or entered in the study. A minimal set of screen failure information is required to ensure transparent reporting of screen failure participants, to meet the Consolidated Standards of Reporting Trials (CONSORT) publishing requirements and to respond to queries from regulatory authorities. Minimal information includes demography, screen failure details, eligibility criteria, and any serious adverse event (SAE).

Individuals who do not meet the criteria for participation in this trial (screen failure) because of normal variability in safety measures may be rescreened one additional time. Rescreened participants should be assigned the same participant number as for the initial screening.

5.5 STRATEGIES FOR RECRUITMENT AND RETENTION

Approximately thirty (30) patients with MGD will be randomized to the study. Based upon data from the LipiFlow® development program a screen failure rate of ~ 40% is expected for new patients. Thus, ~up to 42 patients will need to be screened to achieve ~up to 30 patients randomized to treatment.

All advertisements, if required for subject recruitment, will be submitted to the IEC and approved by the IEC before they are used.

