Number of Patients: Approximately thirty (30) patients with MGD will be randomized to the study. Based upon data from the LipiFlow® development program a screen failure rate of $\sim 40\%$ is expected for new patients. Thus, \sim up to 42 patients will need to be screened to achieve \sim up to 30 patients randomized to treatment.

Condition/Disease: Meibomian Gland Dysfunction (MGD)

Key Inclusion Criteria:

- Male or female, 18 years of age or older at screening visit
- Capable of understanding and willing to provide written informed consent and likely to complete the entire course of study according to instructions
- Written authorization for use and release of health and research study information has been obtained
- Best-corrected visual acuity (BCVA) of 20/40 or better (Snellen equivalent), using the logarithm of the minimum angle of resolution (LogMAR) in each eye at the screening visit
- Evidence of meibomian gland obstruction (based on a meibomian gland secretion (MGS) score of ≤ 12 for 15 glands of the lower lid) in both eyes at the screening visit
- Reported dry eye signs and symptoms within the past 3 months: Ocular Surface Disease Index (OSDI) score ≥ 13 ; TBUT < 10 seconds in both eyes
- Demonstrated ability to follow dosing instructions at the baseline visit
- Prior to the screening visit patients are required to discontinue:
 - Use of systemic antihistamines or isotretinoin for at least 1 month

- Anti-inflammatory treatments for DED (e.g., cyclosporine ophthalmic emulsion [Restasis® or Ikervis®] or lifitegrast ophthalmic solution [Xiidra®]) for at least 3 months
- All other prescription medications used for dry eye or MGD (e.g., antibiotics, corticosteroids, and non-steroidal anti-inflammatory drugs) for at least 2 weeks
- LipiFlow® or other lid-heating therapy, meibomian gland probing, or therapeutic gland expression in either eye within 6 months prior to the screening visit
- All other MGD treatments (e.g., at-home warm compress therapy, eyelid hygiene, eyelid massage, and manual lid expression) for at least 2 weeks

And

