9 STATISTICAL CONSIDERATIONS

9.1 SAMPLE SIZE DETERMINATION

The sample size is determined empirically.

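### Screening 42 patients to randomise 30 does not follow from a 40% screen-failure rate; that rate needs about 50 if all are new and none is rescreened

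*Combined protocol and SAP*

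**What the plan says.** Section 5.5 (Strategies for Recruitment and Retention) gives three linked figures. The target is "Approximately thirty (30) patients with MGD will be randomized to the study". From the LipiFlow development programme, "a screen failure rate of ~ 40% is expected for new patients". The next sentence draws the conclusion: "Thus, ~up to 42 patients will need to be screened to achieve ~up to 30 patients randomized to treatment". The synopsis material in section 1.2, under Number of Patients, makes the same statement ("up to 42 patients will need to be screened to achieve" 30).

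Three other places bear on how to read these figures:

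- Section 5.4 fixes the denominator of the rate: "Screen failures are defined as participants who consent to participate in the clinical trial but are not subsequently randomly assigned to the study intervention". It also allows a limited second attempt: patients who fail "because of normal variability in safety measures may be rescreened one additional time".
- The exclusion criteria in section 5.2 (and in section 1.2) rule out "Participation in another clinical trial involving a therapeutic drug or device within the past 30 days (except for AZR-MD-001"). Recent participants in other studies of this drug may therefore enter, and they might not count as new patients.
- Section 9.1 says only: "The sample size is determined empirically".

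**The concern.** The sentence giving 42 begins with *thus*, so 42 is presented as the result of the 40% rate and the target of 30. Those two inputs give 50. A reader who plans from the text, such as the site or the ethics committee, would expect fewer people to be consented and screened than the protocol's own rate requires.

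What is at stake is recruitment planning. If screening did stop at 42, with only new patients and no rescreening, the trial would expect about 25 randomised patients. Under the 2:2:1:1 allocation, the arms would then be roughly 8:8:4:4 and not 10:10:5:5.

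**Working it through.** **Inputs from the protocol.** Target randomised: 30 (section 5.5). Screen-failure rate: about 40%, stated for new patients (section 5.5). Stated number screened: 42 (sections 5.5 and 1.2). Denominator of the rate: consented participants (section 5.4).

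**1. Where 42 could come from.** Multiplying the target by one plus the rate gives 30 × (1 + 0.40) = 42, exactly the stated figure. That applies the failure rate to the number randomised. By the section 5.4 definition it belongs to the number screened. The match suggests this origin but does not prove it.

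**2. The number the stated rate requires.** Screened = randomised / (1 − failure rate) = 30 / (1 − 0.40) = 30/0.60 = 50. The stated figure is 8 lower, which is 8/50 = 16% of the number needed.

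**3. What 42 would deliver.** 42 × 0.60 = 25.2 expected randomised, or 30 − 25.2 = 4.8 short. If patients pass or fail independently, the binomial probability of randomising at least 30 is 8.6% with 42 screened and 56.1% with 50 screened.

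**4. The failure rate that 42 implies.** 1 − 30/42 = 12/42 = 28.6%.

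**5. Whether the approximation sign covers the gap.** At 35% failure, 30/0.65 = 46.2, so 47 screened. At 30%, 30/0.70 = 42.9, so 43. Even a rate ten points below the stated one does not quite reach 42.

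**6. Whether returning or rescreened patients cover the gap.** The shares and pass rates below are assumptions; the protocol gives none. Let *r* be the share of returning patients, all assumed to pass, and *f* the share of failures rescreened, with 60% of those passing. The overall pass rate is *p* = *r* + (1 − *r*) × 0.60 for returning patients alone, and *p* = 0.60 + 0.40 × *f* × 0.60 for rescreening alone. Numbers needed are rounded up.

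| Assumption | *p* | Expected randomised from 42 | Screened for 30 |
|---|---|---|---|
| All new, no rescreening | 0.600 | 25.2 | 50 |
| *r* = 10% | 0.640 | 26.9 | 47 |
| *r* = 20% | 0.680 | 28.6 | 45 |
| *f* = 10% | 0.624 | 26.2 | 49 |
| *f* = 25% | 0.660 | 27.7 | 46 |
| *r* = 20%, and *f* = 25% among new patients | 0.20 + 0.80 × 0.660 = 0.728 | 30.6 | 42 |

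For 42 to suffice through one route alone, the share needed is:

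- returning patients: *r* = (30/42 − 0.60)/0.40 = 28.6%, with no failures among them;
- rescreening: *f* = (30/42 − 0.60)/0.24 = 47.6% of all failures.

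**The case against.** The strongest defence is that the 40% is given for new patients only. Because earlier AZR-MD-001 participants are not excluded, the qualifier may be deliberate and the intended overall rate may be lower. A blended rate near 29% is possible, and a mix such as 20% returning plus 25% of failures rescreened would make 42 enough. This part of the defence stands: 50 is the right number only if all patients are new and none is rescreened. It does not rescue the sentence, because the protocol states no patient mix and no failure rate for returning patients, and it draws 42 directly from the 40%.

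Rescreening alone is a weaker defence. Section 5.4 limits it to failures caused by normal variability in safety measures. Several entry criteria, such as the meibomian gland secretion score, OSDI, tear break-up time and the washout periods, are not among the safety measures listed in section 8.1.1. A rescreened share near 48% of all failures is therefore hard to assume.

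It can also be said that both figures are hedged as approximate upper limits, so that 25 randomised would still fall within the wording. But the preceding text sets the target at approximately 30, and no reading of approximately turns 50 into 42.

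Finally, nothing scientific rests on 42: no power calculation, analysis set or stopping rule uses it, and the site is free to screen more. This is correct, and it keeps the point minor.

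**Conclusion.** The concern holds as a minor arithmetic error in the recruitment forecast. On the protocol's own rate and its own definition of a screen failure, about 50 patients must be screened to randomise 30. The stated 42 is 8 too few and corresponds to a failure rate of about 29%.

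The figure of 50 rests on all patients being new and none being rescreened. Under the partial departures considered singly (10% or 20% returning, or 10% or 25% of failures rescreened), the requirement is 45 to 49. Only larger or combined departures bring it down to 42, and the documents state none of them. Whichever mix was intended, the stated basis does not support the stated result.

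**What to change.** In section 5.5 and under Number of Patients in section 1.2, replace 42 with approximately 50 screened to randomise approximately 30. If 42 is intended, keep it but state the overall screen-failure rate of about 29% and where it comes from, for example the expected share of returning AZR-MD-001 participants, the expected yield from rescreening, or both.

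The first option changes one number in two places and adds about 8 planned screenings. The second adds one sentence in each place.

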6 STUDY INTERVENTION

6.1 STUDY INTERVENTION(S) ADMINISTRATION

6.1.1 STUDY TREATMENT(S)/ FORMULATION(S)/ MEDICAL DEVICE COMPOSITION OR DESIGN

AZR-MD-001 Ophthalmic Ointment contains the drug product, AZR-MD-001 (1.0%), and suitable excipient. The only excipient in the formulation is White Soft Paraffin (Petrolatum white). The AZR-MD-001 vehicle and product labelled “Vaseline” for use at the baseline visit contain only Petrolatum white. The formulations will be supplied in unit dose containers (see

Table 6.1.1-1).

Table 6.1.1-1 Investigational Product and Packaging / Labelling Characteristics

| | Investigational Product | | |
|---|--|---|---|
| Product name: | AZR-MD-001 sterile ophthalmic ointment (Selenium disulfide API in suspension) | Vehicle | “Vaseline” |
| Formulation description: | AZR-MD-001 is an orange opaque dispersion ointment with an odor faintly of hydrogen sulfide | Placebo ointment will match AZR-MD-001’s texture | Placebo ointment will match AZR-MD-001’s texture |
| Dosage form: | Ophthalmic ointment/semi-solid drug | Ophthalmic ointment/semi-solid drug | Ophthalmic ointment/semi-solid drug |
| Unit dose strength(s)/Dosage level(s): | 1.0%10mg | Placebo Petrolatum, white | Placebo Petrolatum, white |
| Route of Administration | Topical | Topical | Topical |
| Dosing instructions: | Store between 2 – 8°C until opened. Refrigerate. Do not freeze. Stop use 4 weeks (30 days) after opening. Protect from light | Store between 2 – 8°C until opened. Refrigerate. Do not freeze. Stop use 4 weeks (30 days) after opening. Protect from light. | Store between 2 – 8°C until opened. Refrigerate. Do not freeze. Stop use 4 weeks (30 days) after opening. Protect from light. |
| Physical description: | An orange opaque ointment packaged in a multi-use tube | A white opaque ointment packaged in a multi-use tube | A white opaque ointment packaged in a multi-use tube |
| Device: | Multi -use white tube with cap | Multi -use white tube with cap | Multi -use white tube with cap |
| Method for individualizing dosage: | Each container/tube is placed in an individual package and appropriately labelled. | Each container/tube is placed in an individual package and appropriately labelled. | Each container/tube is placed in an individual package and appropriately labelled |

API = Active pharmaceutical ingredient

